5.1.2.3.7 Cardiac Toxicity

QT interval prolongation was observed in the ECG substudy of Study NP22657, the Phase II clinical trial of vemurafenib in patients with previously treated, metastatic melanoma (n= 132). Vemurafenib treatment at a dose of 960 mg BID was associated with a prolongation of the QTc interval in some adult patients with metastatic melanoma,

and the largest mean QTc interval change from baseline noted was 15.1 ms (upper bound of the one-sided 95% CI, 17.7 ms). The extent of change in the QTc interval from baseline was related to the vemurafenib steady-state concentration in plasma. One patient (0.8%) had a QTc interval prolongation >60 ms (Grade 2) compared with baseline, and 2 patients (1.5%) had an absolute QTc interval >500 ms (Grade 3) on at least one occasion. The mean QTc interval prolongation in the study population appeared to remain stable between 12 and 15 ms at all assessment timepoints after Cycle 1, Day 15. To date, there have been no clinical adverse events, manifest cardiac arrhythmias, or other clinically significant cardiac events in clinical trials that are linked to QTc interval prolongation.

As a result of these findings, the following guidelines will be implemented in this study to minimize the risk of ventricular arrhythmia in patients with melanoma treated with vemurafenib in this study:

- Patients with a baseline QTc interval >450 ms or a history of congenital long QT syndrome will not be eligible to participate in this study.
- Triplicate ECG monitoring will occur at baseline and at regular intervals during study treatment (see [Appendix 1](#)).
- Combination therapy with other medications known to lead to prolongation of QTc interval should be avoided, if possible.

Dose Interruption and Permanent Discontinuation for QTc Prolongation

If QTc exceeds 500 ms (measured in triplicate ECG) but is less than or equal to a 60-ms increment compared with baseline OR the change from baseline is greater than 60 ms without QTc >500 ms, study drug treatment should be temporarily interrupted.

If QTc increases to 500 ms AND the change from baseline exceeds 60 ms, study drug treatment should be permanently discontinued. Such patients will NOT be able to restart the study.

Assessment and Management of QTc Prolongation

Immediate action upon observation of QTc >500 ms:

- Both the QTc interval and serum electrolytes with appropriate correction should be monitored regularly until there is clear evidence that the QTc is <500 ms. Patients should remain under close observation until the QTc returns to <500 ms and/or discharge is considered appropriate by consulting cardiologist.
- Serum electrolytes (particularly potassium, magnesium, and corrected calcium) must be evaluated, and any and all electrolyte abnormalities, with particular attention to hypokalemia, hypomagnesemia, and hypocalcemia, must be corrected.
- Patients must be closely monitored and, in particular, re-evaluated for other cardiac risk factors (e.g., hypertension, congestive heart failure, cardiac ischemia, bradyarrhythmias, diabetes). Any other treatable risk factors (e.g., hypothyroidism) should be corrected per standard of care.

- All concomitant medications must be re-evaluated, and consideration should be given to discontinuing those that could prolong the QTc interval and, if appropriate, substituting them with an alternative medication that does not affect the QTc interval.
- Patients must have ECG re-evaluated within 48 hours to ensure QTc interval is improving after interruption of study medication and correction of aforementioned potential concomitant factors.
- Study treatment will not be resumed until the QTc is clearly <500 ms. Upon resumption of study drug treatment, the study drug dose should be reduced. Refer to [Table 2](#).
- Upon resumption of study drug treatment, ECG (measured in triplicate) and electrolytes should be monitored at Day 1 (i.e., day when study drug is resumed) pre-dose, then every 2 weeks (± 3 days) for at least two cycles, then Day 1 (± 3 days) of the following cycle, and then Day 1 (± 3 days) of every subsequent third cycle. This replaces the protocol-mandated ECG monitoring that is outlined in [Appendix 1](#).
- A cardiologist must be consulted if any of the following occurs:
 - The QTc does not return to baseline upon temporary or permanent interruption of study drug or upon correction of secondary causes (e.g., electrolyte abnormalities, concomitant medications known to prolong QT, cardiac ischemia, severe bradycardia).
 - There are concomitant signs or symptoms of potential pro-arrhythmia (e.g., premature ventricular contractions [PVCs], persistent bradycardia, syncope, palpitations, etc.).
 - The physician is not comfortable managing prolonged QTc according to the guidelines outlined above.

For all patients with QTc change from baseline >60 ms, without QTc >500 ms:

- Serum electrolytes (particularly potassium, magnesium, and corrected calcium) should be evaluated, and any and all electrolyte abnormalities, with particular attention to hypokalemia, hypomagnesemia, and hypocalcemia, must be corrected.
- Patients should be closely monitored and in, particular, re-evaluated for other cardiac risk factors (e.g., hypertension, congestive heart failure, cardiac ischemia, bradyarrhythmias, diabetes). Any other treatable risk factors (e.g., hypothyroidism) should be corrected per standard of care.
- All concomitant medications should be re-evaluated, and consideration should be given to discontinuing those that could prolong the QTc interval and, if appropriate, substituting them with an alternative medication that does not affect the QTc interval.
- Both the QTc interval and serum electrolytes (with appropriate correction) should be monitored weekly until the QTc change from baseline is less than 60 ms before resuming therapy.

- Upon resumption of study drug treatment, the study drug dose should be reduced. Refer to [Table 2](#).

Upon resumption of study drug treatment, the ECG (measured in triplicate) and electrolytes should be monitored at Day 1 (i.e., day when study drug is resumed) pre-dose, then every 2 weeks (± 3 days) for at least two cycles, then Day 1 (± 3 days) of the following cycle, and then Day 1 (± 3 days) of every subsequent third cycle. This replaces the protocol-mandated ECG monitoring that is outlined in [Appendix 1](#).

- A cardiologist must be consulted if any of the following occurs:

The QTc does not return to baseline upon temporary or permanent interruption of study drug or upon correction of secondary causes (e.g., electrolyte abnormalities, concomitant medications known to prolong QT, cardiac ischemia, severe bradycardia).

There are concomitant signs or symptoms of potential pro-arrhythmia (e.g., PVCs, persistent bradycardia, syncope, palpitations, etc.).

The physician is not comfortable managing prolonged QTc according to the guidelines outlined above.

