4.6.1.1 Discontinuation from Study Drug

Patients are to receive study drug for up to 52 weeks. Patients must discontinue study drug if they experience any of the following:

- Pregnancy
- Histopathologic confirmation of occurrence of a new primary melanoma (diagnosed by Roche-designated central pathology laboratory). Refer to Section 5.1.2.3 for a discussion on new primary melanoma
- Histopathologic confirmation of recurrent melanoma
- Radiographic and/or histopathologic findings consistent with recurrence of melanoma in brain
- Radiographic findings consistent with recurrence when suspicious lesions are deemed not amenable to biopsy by the investigator or the patient refuses biopsy confirmation

Patients who discontinue study drug prematurely will be asked to return to the clinic for an end-of-treatment visit (see Section 4.5.2.2, Section 4.5.2.3 and Appendix 1) and may undergo follow-up assessments (see Section 4.5.2.2, Section 4.5.2.3, Section 4.5.2.4, and Appendix 1). The primary reason for premature study drug discontinuation should

be documented on the appropriate eCRF. Patients who discontinue study drug prematurely will not be replaced.

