5.1.3 Management of Specific Adverse Events

Management of symptomatic adverse events or QTc prolongation may require temporary interruption, dose reduction, or treatment discontinuation of study drug (see [Table 2](#)). Dose modifications or interruptions are not recommended for cuSCC/KA adverse events. Dose modifications or interruptions should occur in accordance with the schedule below, regardless of causality determination.

Table 2 Dose Modification Schedule

Grade ^a	Recommended Dose Modification ^b
Grade 1 or Grade 2 (tolerable) ^c	Maintain study drug at a dose of 4 tablets twice daily
Grade 2 (intolerable) ^c or Grade 3	
First appearance	Interrupt treatment until Grade 0 or 1. Resume dosing at 3 tablets twice daily
Second appearance	Interrupt treatment until Grade 0 or 1. Resume dosing at 2 tablets twice daily
Third appearance	Discontinue permanently
Grade 4	
First appearance	Discontinue permanently or interrupt study drug treatment until Grade 0 or 1. Resume dosing at 2 tablets twice daily
Second appearance	Discontinue permanently

^a The intensity of clinical adverse events graded by the National Cancer Institute Common Terminology Criteria for Adverse Events, Version 4.0.

^b No dose modification is required in the setting of an isolated increase in gamma glutamyl transferase in the absence of a transaminitis, elevated serum bilirubin, or other hepatic symptoms.

^c All Grade 2 liver function test abnormalities will be defined as “intolerable.”

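### Protocol Section 5.1.2.3.7 and Table 2 give different instructions for some QTc events, Section 5.1.2.3.7 overlaps itself at exactly 500 ms, and nothing says which text governs

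*Protocol*

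**What the plan says.** Protocol Section 5.1.2.3.7 has a subheading of its own for QTc-related interruption and discontinuation, with three branches:

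- **QTc above 500 ms, change of 60 ms or less:** temporary interruption. The condition reads "If QTc exceeds 500 ms (measured in triplicate ECG) but is less than or equal to a 60-ms increment compared with baseline".
- **Change above 60 ms, QTc not above 500 ms:** also temporary interruption: "the change from baseline is greater than 60 ms without QTc >500 ms, study drug treatment should be temporarily interrupted".
- **Both raised:** "If QTc increases to 500 ms AND the change from baseline exceeds 60 ms, study drug treatment should be permanently discontinued". It adds: "Such patients will NOT be able to restart the study".

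For resumption after QTc above 500 ms, the same section says "Study treatment will not be resumed until the QTc is clearly <500 ms". It refers to Table 2 for the reduced dose.

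Section 5.1.3 introduces Table 2 with "Management of symptomatic adverse events or QTc prolongation may require temporary interruption, dose reduction, or treatment discontinuation of study drug" and says that modifications should follow the schedule. The stated exceptions are cuSCC/KA, in the text, and an isolated GGT rise, in footnote b. Footnote c classes all Grade 2 liver test abnormalities as intolerable. There is no QTc row, exception or footnote. For the first appearance of an intolerable Grade 2 or any Grade 3 event, the table says "Interrupt treatment until Grade 0 or 1. Resume dosing at 3 tablets twice daily". For a tolerable Grade 2 event it keeps the full dose.

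Sections 1.2.5 and 5.1.2.3.7 both label QTc above 500 ms as Grade 3 and a change above 60 ms as Grade 2.

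**The concern.** Section 5.1.3 brings QTc prolongation under Table 2 without giving way to Section 5.1.2.3.7, and Section 5.1.2.3.7 does not claim priority over the table. A site that reads both can find two instructions for one ECG.

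Grade 3 or higher QT prolongation is an adverse event of special interest (Protocol Section 5.2.3), and ECG change is a safety outcome (Section 3.4.2). The SAP summarises reasons for premature discontinuation (Section 4.2), dose reductions and interruptions (Section 4.7.1), and adverse events leading to discontinuation (Section 4.7.2). If compliant sites handled the same ECG differently, those counts for QTc events would partly reflect which passage the site followed.

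**Working it through.** The documents give no figure to reproduce for this point. The check sets the two texts side by side, using only the grades that the protocol assigns. It assumes that the permanent-stop branch covers values above 500 ms as well as 500 ms itself.

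| QTc | Change from baseline | Section 5.1.2.3.7 | Table 2, first appearance | Result |
|---|---|---|---|---|
| >500 ms | >60 ms | Discontinue permanently, no restart | Grade 3: interrupt, resume at reduced dose | Conflict |
| >500 ms | ≤60 ms | Interrupt, resume at reduced dose | Grade 3: interrupt, resume at reduced dose | Same action |
| exactly 500 ms | >60 ms | Discontinue and interrupt both apply | Grade 2: maintain if tolerable | Section contradicts itself |
| <500 ms | >60 ms | Interrupt | Grade 2: maintain if tolerable, interrupt if not | Conflict if tolerable |

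The first row does not depend heavily on the grade. No first-appearance row in Table 2 makes permanent discontinuation mandatory; even Grade 4 offers resumption as an alternative.

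**Reach of the first conflict.** Entry requires a baseline QTc of 450 ms or less. For QTc above 500 ms with a change of 60 ms or less:

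baseline ≥ QTc − 60 > 500 − 60 = 440 ms.

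The agreeing branch therefore needs a baseline above 440 and up to 450 ms, with QTc no higher than 450 + 60 = 510 ms. For a baseline of 440 ms or less, every QTc above 500 ms is a change above 60 ms and falls in the conflict. Example: baseline 420 ms, on-treatment 510 ms, change 510 − 420 = 90 ms.

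**Reach of the 500 ms overlap.** At exactly 500 ms, a change above 60 ms needs a baseline below 500 − 60 = 440 ms. Every such patient meets both branches.

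**How many patients.** Inputs from Sections 1.2.5 and 5.1.2.3.7, Phase II study, n = 132:

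- QTc above 500 ms: 2/132 = 1.5%.
- Change above 60 ms: 1/132 = 0.8%.
- Both conditions: at most min(2, 1) = 1, and possibly 0.

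With about 475 patients randomised 1:1, the vemurafenib arms hold about 475/2 = 237.5.

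- If 1/132: 237.5 × 1/132 = 1.8 patients. The exact (Clopper-Pearson) 95% interval for 1/132 is 0.02% to 4.15%; at the upper limit, 237.5 × 0.0415 = 9.9.
- If 0/132: point estimate 0. The upper limit is 2.76%, and 237.5 × 0.0276 = 6.6.

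**Resumption.** Section 5.1.2.3.7 asks for QTc clearly below 500 ms or, after a change above 60 ms, a change below 60 ms. Table 2 asks for Grade 0 or 1. The documents cite CTCAE v4.0 but do not give its upper QTc limit for Grade 1. If that limit is assumed to lie between 450 and 500 ms, the gap could be anywhere from 50 ms to 0 ms, so none is shown.

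**The case against.** The strongest reply is that the specific rule naturally overrides the generic one:

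- Section 5.1.2.3.7 has a dedicated QTc subheading, and Appendix 1 footnote z repeats its interruption triggers.
- It cites Table 2 only at the dose-reduction step, whereas the hepatic section expressly sends its interruption rules to Table 2.
- Table 2 is a general schedule whose column is headed as recommended, and its lead-in lists discontinuation as a possible QTc outcome.

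Much of this stands. A reader might infer that the rule cannot be applied consistently at all; the documents do not support that. But precedence is nowhere stated, Section 5.1.3 tells sites to follow the schedule, and footnote z does not repeat the permanent stop. Preferring Section 5.1.2.3.7 also leaves its own overlap at 500 ms.

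Other stronger readings fail:

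- **Resumption thresholds.** They are worded differently, but being below 500 ms is a minimum condition that can be met together with Table 2, and no numerical gap can be shown.
- **Section 4.6.1.1.** Its list opens "Patients must discontinue study drug if they experience any of the following" and omits QTc, but it is not exhaustive. It also omits the dosing break of more than 28 days, prohibited therapies and Table 2's own permanent stops.
- **Larger counts.** Scaling all patients above 500 ms gives 237.5 × 2/132 = 3.6, but at least one of those two had a change of 60 ms or less, where the texts agree. Patients peaking at 481 to 500 ms (6 − 2 = 4 of 132, or 7.2 when scaled) do not trigger either rule by that value alone.
- **Nearly all events above 500 ms.** The result for baselines of 440 ms or less concerns baseline values. It does not count patients, and the Phase II data do not bear out the wider statement.
- **Urgency for current patients.** The Version 10 amendment rationale dates the last dose to 14 September 2016, so nobody can now be stopped or re-challenged under this text.

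**Conclusion.** The inconsistency is real but limited to three situations: QTc above 500 ms with a change above 60 ms; exactly 500 ms with a change above 60 ms; and a tolerable Grade 2 change above 60 ms without QTc above 500 ms. For QTc above 500 ms with a change of 60 ms or less, the texts agree on the action.

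The first conflict would be expected in about 2 of roughly 237 vemurafenib patients, with a range of 0 to about 10. This assumes that Phase II rates carry over to the adjuvant setting. The documents do not give the baseline QTc limit used in that study.

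Severity is moderate. A stated safety rule contradicts another passage and is ambiguous at its own threshold, and the remaining consequence is for interpreting descriptive safety and exposure summaries. DFS is analysed by randomised arm in all patients, so the DFS analysis, alpha and power are unaffected. Nothing here indicates which clinical rule is right.

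**What to change.** 1. Reconcile Section 5.1.2.3.7 with Table 2. Add a Table 2 footnote stating which passage governs QTc events, as footnote b does for GGT.
2. Rewrite the QTc branches with limits that do not overlap, so that each combination of QTc and change from baseline falls in exactly one branch.
3. Leave the choice of rule to the sponsor's safety physicians.
4. Since dosing has ended, report for each QTc event the QTc, the change from baseline, the action taken and which passage was followed. Place this beside the summaries of discontinuations, interruptions and dose reductions in SAP Sections 4.2, 4.7.1 and 4.7.2.

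The cost is protocol wording and one short listing, with no extra visits or tests. Where a site did not record which passage it followed, the listing should say so.

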5.1.3 Management of Specific Adverse Events

Management of symptomatic adverse events or QTc prolongation may require temporary interruption, dose reduction, or treatment discontinuation of study drug (see [Table 2](#)). Dose modifications or interruptions are not recommended for cuSCC/KA adverse events. Dose modifications or interruptions should occur in accordance with the schedule below, regardless of causality determination.

Table 2 Dose Modification Schedule

Grade ^a	Recommended Dose Modification ^b
Grade 1 or Grade 2 (tolerable) ^c	Maintain study drug at a dose of 4 tablets twice daily
Grade 2 (intolerable) ^c or Grade 3	
First appearance	Interrupt treatment until Grade 0 or 1. Resume dosing at 3 tablets twice daily
Second appearance	Interrupt treatment until Grade 0 or 1. Resume dosing at 2 tablets twice daily
Third appearance	Discontinue permanently
Grade 4	
First appearance	Discontinue permanently or interrupt study drug treatment until Grade 0 or 1. Resume dosing at 2 tablets twice daily
Second appearance	Discontinue permanently

^a The intensity of clinical adverse events graded by the National Cancer Institute Common Terminology Criteria for Adverse Events, Version 4.0.

^b No dose modification is required in the setting of an isolated increase in gamma glutamyl transferase in the absence of a transaminitis, elevated serum bilirubin, or other hepatic symptoms.

^c All Grade 2 liver function test abnormalities will be defined as “intolerable.”

5.2 SAFETY PARAMETERS AND DEFINITIONS

Safety assessments will consist of monitoring and recording adverse events, including serious adverse events and non-serious adverse event of special interest, protocol-specified safety laboratory assessments, vital signs, and other protocol-specified tests that are deemed critical to the safety evaluation of the study.

Certain types of events require immediate reporting to the Sponsor, as outlined in Section 5.4.

5.2.1 Adverse Events

According to the ICH guideline for Good Clinical Practice, an adverse event is any untoward medical occurrence in a clinical investigation subject administered a pharmaceutical product, regardless of causal attribution. An adverse event can therefore be any of the following:

- Any unfavorable and unintended sign (including an abnormal laboratory finding), symptom, or disease temporally associated with the use of a medicinal product, whether or not considered related to the medicinal product
- Any new disease or exacerbation of an existing disease (a worsening in the character, frequency, or severity of a known condition)

- Recurrence of an intermittent medical condition (e.g., headache) not present at baseline
- Any deterioration in a laboratory value or other clinical test (e.g., ECG, X-ray) that is associated with symptoms or leads to a change in study treatment or concomitant treatment or discontinuation from study drug
- Adverse events that are related to a protocol-mandated intervention, including those that occur prior to assignment of study treatment (e.g., screening invasive procedures such as biopsies)

5.2.2 Serious Adverse Events (Immediately Reportable to Roche)

A serious adverse event is any adverse event that meets any of the following criteria:

- Fatal (i.e., the adverse event actually causes or leads to death)
- Life threatening (i.e., the adverse event, in the view of the investigator, places the patient at immediate risk of death)

This does not include any adverse event that, had it occurred in a more severe form or was allowed to continue, might have caused death.

- Requires or prolongs inpatient hospitalization (see Section 5.3.5.9)
- Results in persistent or significant disability/incapacity (i.e., the adverse event results in substantial disruption of the patient’s ability to conduct normal life functions)
- Congenital anomaly/birth defect in a neonate/infant born to a mother exposed to study drug
- Significant medical event in the investigator's judgment (e.g., may jeopardize the patient or may require medical/surgical intervention to prevent one of the outcomes listed above)

A new primary malignancy (other than cuSCC/KA) or progression or recurrence of a prior malignancy (other than the disease under study) will be categorized as a serious adverse event.

Recurrence of melanoma is not reported as an adverse event if it is clearly consistent with the suspected recurrence of the disease under study. Clinical signs or symptoms of recurrence may be reported as adverse events only if the symptom cannot be determined as exclusively due to the recurrence of the underlying malignancy or does not fit the expected pattern of recurrence for the disease under study. If there is any uncertainty about an adverse event being due only to the extent of the disease under study, it should be reported as an adverse event or a serious adverse event.

The terms “severe” and “serious” are not synonymous. Severity refers to the intensity of an adverse event (rated as mild, moderate, or severe, or according to NCI CTCAE; see Section 5.3.3); the event itself may be of relatively minor medical significance (such as severe headache without any further findings).

Severity and seriousness need to be independently assessed for each adverse event recorded on the eCRF.

Serious adverse events are required to be reported by the investigator to the Sponsor within 24 hours after learning of the event (see Section 5.4.2 for reporting instructions).

